#### 2.4 Sample Size Determination

To test the primary hypothesis for the proof of concept, an alternating logistic regression will be used to compare the proportion of live female adult worms without *Wolbachia* at Month 6 between each of the four active arms (Arm A, B, C, or D) and the control arm (Arm E), taking into account the clustering of this worm-level endpoint by subject. Using simulations that add substantial clustering by subject to the endpoint values and assuming the number of worms in each subject varies from 1 to 10, following the multinomial distribution with probability = (0.20, 0.16, 0.16, 0.16, 0.08, 0.08, 0.08, 0.03, 0.03, 0.02) for values (1, 2, 3, 4, 5, 6, 7, 8, 9, 10), 17 subjects will provide 88% power to detect the difference between an active arm (Arm A, B, C, or D) where 70% of worms are without *Wolbachia* (2-sided  $\alpha = 0.10$ ). The clustering of the endpoint values by subject is provided by the Pearson intraclass correlation coefficient (ICC) for binary outcomes and was given as ICC = 0.54 for simulated arms where 70% or 30% of the worms are without *Wolbachia*.

To test the primary hypothesis for the combination rule, an alternating logistic regression will be used to compare the proportion of live female adult worms without *Wolbachia* at Month 6 between the combination arm (Arm C or D) and the two single drug arms (Arm A and E) separately, 25 subjects per arm will provide 81% power to detect the difference between the combination arm where 90% of worms are without *Wolbachia* and the single drug arm where 70% of worms are without *Wolbachia* (2-sided  $\alpha = 0.10$ ). ICC = 0.54 was added to the simulated arm where 70% of the worms are without *Wolbachia*. Minimal clustering (ICC = 0.01) was added to the simulated arm where 90% of the simulated arm where 90% of the worms are without *Wolbachia* because there would be little variation among subjects with an overall high response rate. 30 subjects will be enrolled per arm to account for 17% drop out by Month 6.

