#### 9.3.2 Main Analysis of Primary Efficacy Endpoint

The primary efficacy endpoint will be compared between the following pairs of treatment arms for the PP population in Part 1:

- For proof of concept: (1) A vs. E, (2) B vs. E, (3) C vs. E, (4) D vs. E;
- For satisfying the combination rule: if Arm C is to advance to Study B18-894/DNDi-TYL-01 Part 2, then (1) C vs. A, (2) C vs. E; if Arm D is to advance to Part 2 but Arm C is not, then: (1) D vs. A, (2) D vs. E.

The comparisons will be conducted using contrasts from an alternating logistic regression model that includes all the five treatment arms as factors. The alternating logistic regression will account for within-subject association of the worm-level endpoint by estimating the pairwise log odds ratio (different than the odds ratio of the primary estimand) of a worm's Wolbachia status in relation to another worm's Wolbachia status within each subject. In this regression model, the within-subject association is estimated with one parameter. That is, the pairwise log odds ratios used to account for the within-subject association are assumed as equal for all pairs of worms within a subject, and the same log odds ratios are assumed for all subjects in the same treatment arm. However, different log odds ratios/parameters are assumed in different treatment arms, allowing for arm-specific within-subject associations. If the model does not converge, the within-subject associations for the five treatment arms will be assumed as the same. If the model still does not converge, a generalized linear mixed model will be used instead of the alternating logistic regression model. The mixed model will assume the framework of a logistic regression using a random intercept for each subject to account for the within-subject association of the worm-level endpoint. The variance of the random intercepts will be assumed as different for the five treatment arms.

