Odds ratios with p-values and 95% confidence intervals for each of the pairwise comparisons will be reported. In addition, the percentages of live female adult worms without *Wolbachia* out of all live female adult worms from subjects in the PP population will also be summarized by treatment arm with 95% Wilson's score confidence intervals for all the percentages. The numerator and denominator of the percentage will be a sum across all subjects in a treatment arm. The rules of Section 9.2 for imputing missing data in the PP population worms will be applied; any worms that still have missing *Wolbachia* status after that will be excluded from both the numerator and denominator.

The attributes of the estimands corresponding to the primary efficacy endpoint are summarized in Table 1.

		A	Attributes of the	e Estimand	
Estimand Label	Treatment	Endpoint	Population	Handling of Intercurrent Events	Statistical Summary
Proof of concept	Arm A: ABBV-4083 for 7 days Arm B: ABBV-4083 for 14 days Arm C: ABBV-4083 for 7 days + albendazole for 7 days Arm D: ABBV-4083 for 7 days + albendazole for 3 days Arm E: albendazole for 7 days	Status of depletion of Wolbachia in each live female adult worm, evaluated using nodules collected at Month 6	PP population: all subjects who completed treatment and did not take prohibited medication, who had Month 6 nodulectomy with female worms	IE1: Subjects who did not complete treatment (6 out of 7 days for Arms A, C, E, 12 out of 14 days for Arm B, 6 out of 7 days of ABBV-4083 and all 3 days of albendazole for Arm D) will be excluded. IE2: Subjects who did not have Month 6 nodulectomy data will be excluded. IE3: Subjects who took prohibited medications will be excluded.	Odds ratio of Wolbachia depletion in live female adult worms in subjects taking active regimen vs. control regimen
Satisfying the combination rule	Arm A Arm C (or D depending on Part 2 regimens) Arm E	Same as above	Same as above	Same as above	Odds ratio of Wolbachia depletion in live female adult worms in subjects taking the combination regimen vs. the single drug regimens

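### The last fallback for the Part 1 primary model (SAP 9.3.2) replaces a population-average odds ratio with a subject-specific one in all five arms, and no rule covers an arm at 0% or 100% depletion

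*SAP*

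**What the plan says.** SAP 9.3.2 sets the main analysis in three steps, and non-convergence is the only trigger for moving on.

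- **Step 1.** "The comparisons will be conducted using contrasts from an alternating logistic regression model" "that includes all the five treatment arms as factors", with a separate within-subject association for each arm.
- **Step 2.** "If the model does not converge, the within-subject associations for the five treatment arms will be assumed as the same".
- **Step 3.** "If the model still does not converge, a generalized linear mixed model will be used instead of the alternating logistic regression model". It is a logistic model with a random intercept per subject, and "The variance of the random intercepts will be assumed as different for the five treatment arms".

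Whichever step is used, "Odds ratios with p-values and 95% confidence intervals for each of the pairwise comparisons will be reported". The arm percentages shown beside them are pooled over worms: "The numerator and denominator of the percentage will be a sum across all subjects in a treatment arm". Table 1 gives the summary measure only as an odds ratio, without saying whether it is population-average or subject-specific. No test statistic is named.

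Protocol 10.5 names ALR and has no fallback. Neither document has a rule for an arm with all or none of its worms depleted. The SAP's only sparsity rule, in 9.2, concerns the imputation model.

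**The concern.** ALR models the arm-level proportion, so its odds ratio compares worms across whole arms and agrees with the pooled percentages. The step 3 coefficient compares odds at the centre of each arm's subject distribution. With clustering the two differ. With a different variance in each arm the gap can go either way, and equal arm proportions no longer imply an odds ratio of 1. A reader could see 90% and 70% beside an odds ratio of 1.43, or 70% and 30% beside 43.4. Because the whole model is replaced, contrasts that caused no fitting problem change target as well.

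The second gap is the uniform arm. The SAP requires an odds ratio, p-value and confidence interval for every pair, but such an arm has no finite odds ratio under any step.

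At stake are the four proof-of-concept contrasts with Arm E and the combination-rule contrasts. Under Protocol 3.3 the combination rule bears on whether Part 2 follows the Base Scenario (294 subjects) or the Alternative Scenario (336).

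**Working it through.** **Inputs (SAP 2.4, 9.1).** Two-sided alpha is 0.10. Worm counts run from 1 to 10 with the stated probabilities (mean 3.79). Depletion is 70% in a single-drug arm, 30% in Arm E and 90% in a combination arm. The SAP gives "ICC = 0.54 for simulated arms where 70% or 30% of the worms are without" Wolbachia, and 0.01 for the 90% arm. With 17% dropout, 30 x 0.83 = 24.9, so about 25 subjects per arm are analysed.

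**The plan's own power.** Simulated ALR reproduces 88% for 70% v 30% with 17 per arm (87.4-89.0% over the variants tried). It reproduces 81% for 90% v 70% with 25 per arm when a common association is used (80.7-81.9%).

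**Marginal odds ratios, steps 1-2.**
- C v A: (0.9/0.1)/(0.7/0.3) = 3.86.
- A v E: (0.7/0.3)/(0.3/0.7) = 5.44.
- Both arms at 70%: 1.00.

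**Subject-specific odds ratios, step 3.** For each arm, take logit(q) normal with mean m and SD s. Solve E(q) = p and Var(q)/[p(1-p)] = ICC.

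| Arm rate, ICC | m | s |
|---|---|---|
| 90%, 0.01 | 2.241 | 0.33 |
| 70%, 0.54 | 1.885 | 3.13 |
| 30%, 0.54 | -1.885 | 3.13 |
| 70%, 0.01 | 0.857 | 0.22 |

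- C v A: exp(2.241 - 1.885) = 1.43.
- A v E: exp(2 x 1.885) = 43.4.
- Both at 70%, ICC 0.01 v 0.54: exp(0.857 - 1.885) = 0.36.

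The gap depends on the ICCs. With Arm C at ICC 0.10, 0.25 and 0.54, the subject-specific C v A value is 2.03, 3.85 and 33.9. With ICC 0.25 in both arms, A v E is 9.95.

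**Power for C v A at planning values, 25 per arm.** The simulations took either all trials or only those in which Arm E came out at 0% (true rate 2%, assumed).

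| Analysis | Power |
|---|---|
| Mixed model, maximum likelihood | 12-17% |
| Mixed model, pseudo-likelihood | 56-61% |
| Marginal GEE, independence | 77-81% |

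In 300 maximum-likelihood fits the odds ratio fell below 1 in 34%. With ICC 0.25 in Arm C, where the two odds ratios agree, maximum likelihood still gave 17-18% against 72% for GEE. So imprecision explains part of the loss. For A v E power is kept (92% against 91-93%), but the median maximum-likelihood odds ratio was 45-56 instead of 5.5-6.0.

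**Uniform arm.** If every worm is depleted, the marginal estimating equation is a sum of positive weights times n(1 - p), which is positive for every p < 1. It has no finite solution on the logit scale. The mixed-model negative log-likelihood also keeps falling: 12.1, 0.03 and 0.0000002 at intercepts 2, 8 and 20. Contrasts between the other arms remain estimable.

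**How often.** With a = p(1-ICC)/ICC and b = (1-p)(1-ICC)/ICC, a subject with k worms has all of them depleted with probability B(a+k, b)/B(a, b). Averaging over k and raising to the power 25 gives:

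| True rate | ICC 0.01 | ICC 0.54 |
|---|---|---|
| 90% | 0.01% | 1.0% |
| 95% | 1.0% | 10.3% |
| 98% | 15.8% | 40.6% |

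By symmetry the same holds for 10%, 5% and 2% with no worm depleted. At planning values nearly all the risk comes from Arms C and D: 2 x 0.000113 = 0.0002, or 0.02% of trials.

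**What software may do.** With one arm at 100%, GEE software used as a stand-in for ALR reported convergence, with a log odds ratio of 27.5-30.7 and a robust SE of about 0.44.

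**The case against.** The strongest objection is that step 3 may never be reached. It needs a convergence failure, and in the checks with GEE as a stand-in, software reported convergence whenever one arm was uniform. SAS behaviour for ALR was not checked. This stands: the route to step 3 is unverified, and the low C v A power is conditional on getting there. It does not remove the defect. A pre-specified step should estimate what the plan intends if it is used, and an unflagged fit with a huge odds ratio and a spuriously small SE is a fault of its own.

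Second, the rates that make a uniform arm realistic are not in the documents. Protocol 2.4.1 expects albendazole alone not to affect Wolbachia levels, but that is not a statement about the share of worms without Wolbachia, and planning assumes 30%. This stands.

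Third, the SAP names no estimation method for the mixed model, and the loss of power is much smaller with pseudo-likelihood. This stands too.

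A reader might infer that a fully depleted combination arm would fail to show superiority and so push Part 2 into the Alternative Scenario. The documents do not support that. Protocol 3.3 refers to statistical superiority, but the SAP names no test. For Arm C at 100% against a 70% arm, a score or permutation test rejected in 100% of simulated trials and a mixed-model likelihood-ratio test in 79-80%. The Wald test from an apparently converged GEE also rejected in 100%, on a meaningless SE. In addition, Protocol 10.9 bases regimen selection on all Part 1 data.

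Finally, Part 1 is an unadjusted proof of concept, and Wilson intervals already describe a uniform arm. That limits the weight of the point, but those intervals give no between-arm test.

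**Conclusion.** The concern holds in two parts. First, step 3 changes the odds ratio for all five arms. At the SAP's own rates and ICCs the change is large, runs in different directions for different contrasts, and moves the null when clustering differs between arms. The values assume normal random intercepts, as in the usual form of such a model, and would shift with other ICCs. Second, a uniform arm has no finite odds ratio at any step and no rule covers it. Depending on the software, it either triggers step 3 or passes unflagged.

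The practical risk is conditional. At planning rates a uniform arm is very unlikely. It becomes realistic only if a true rate is about 95% or above, or 5% or below, which is an assumption. Any effect on the superiority decision in Protocol 3.3 depends on the test used and is not established. The sponsor should still make the change, because it costs little and is best settled before Part 1 is unblinded.

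**What to change.** 1. In SAP 9.3.2, replace step 3 with a marginal logistic GEE with independence working correlation and subject-clustered robust SE, naming the small-sample correction.
2. In Table 1, state that the odds ratio is population-average.
3. Add a rule triggered by the data pattern, not by a convergence flag. If all worms in an arm have the same status, report the odds ratios for its contrasts as not estimable and show the arm percentages. Test those contrasts at two-sided 0.10 with a permutation test that reassigns whole subjects and compares the proportion of worms depleted. Fit the remaining contrasts without that arm.
4. For the supplementary ITT repeat (SAP 9.2 and 9.3.3), report the affected odds ratios as not estimable with descriptive percentages. Pooling permutation results over the 30 imputations is not proposed, because its error rate has not been checked.

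The cost is a few sentences and no new data. Two downsides should be stated in the SAP. The new step 3 is slightly less efficient (C v A power about 77-81%, against 81-83% for step 2). The permutation test is liberal when clustering is very unequal (ICC 0.01 v 0.54): at nominal 10% its error is about 10-11% with both arms at 70%, and about 15-17% with both near 95%. With equal ICCs (0.25 or 0.54 in both arms, both at 95%) it is about 9-10%.

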# Table 1.Summary of the Estimand Attributes of the Primary Efficacy
Endpoint

# 9.3.3 Sensitivity and Supplementary Analyses of the Primary Efficacy Endpoint

As supplementary analyses of the primary endpoint, the same analyses listed in Section 9.3.2 will be repeated for the ITT population following the imputation rules for the missing *Wolbachia* depletion results at Month 6 (Section 9.2).

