#### 9.6 Efficacy Subgroup Analyses

The percentages of live female adult worms without *Wolbachia* out of all live female adult worms from subjects in the PP population will be summarized by treatment arm for each category of the following subgroup variables, after applying the rules of Section 9.2 for missing data. 95% Wilson's score confidence intervals will be provided for all the percentages if the denominator is  $\geq 10$ . The rules of Section 9.2 for imputing missing data in the PP population worms will be applied; any worms that still have missing *Wolbachia* status after that will be excluded from both the numerator and denominator. The subgroup variables include:

- Operable sites with onchocercomata (0, 1, or > 1),
- Baseline skin microfilarial density ( $\leq 5 \text{ or} > 5 \text{ mf/mg}$ ),
- Number of previous ivermectin rounds (0, 1, or > 1)
- Time since the last ivermectin administration ( $\leq 1$  year or > 1 year)
- District of residence (Kimpese, Masa, Masi-Manimba, Moanza, Nsonampangu, Pay Kongila, or Other)

The different treatment effects across these subgroup variables will be further explored using the alternating logistic regression model detailed in Section 9.3.2. The continuous values of the subgroup variables will be used except for district of residence. Each subgroup variable will be added separately to the model as a factor in addition to the treatment arms. Then, the interaction term of the subgroup variable with the treatment arms will be included in addition to the main effect term and analyzed in a separate model to examine the effect of the subgroup variables on treatment efficacy.

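### The 95% Wilson intervals on pooled worm percentages (SAP 9.3.2, 9.6) ignore clustering by subject and cover about 72% at the plan's ICC of 0.54

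*SAP*

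**What the plan says.** The primary endpoint is the Wolbachia status of each live female worm, with several worms per subject.

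- **Odds ratios (SAP 9.3.2).** "The alternating logistic regression will account for within-subject association of the worm-level endpoint by estimating the pairwise log odds ratio" of one worm's status on another's within a subject.
- **Per-arm percentages (SAP 9.3.2).** These get 95% Wilson "score confidence intervals for all the percentages. The numerator and denominator of the percentage will be a sum across all subjects in a treatment arm". No allowance for clustering is stated.
- **ITT (SAP 9.3.3).** Here "the same analyses listed in Section 9.3.2 will be repeated for the ITT population", so the same intervals appear again.
- **Subgroup percentages (SAP 9.6).** 95% Wilson "score confidence intervals will be provided for all the percentages if the denominator is" at least 10, and the denominator is worms. One subgroup variable has seven levels: "District of residence (Kimpese, Masa, Masi-Manimba, Moanza, Nsonampangu, Pay Kongila, or Other".
- **Subgroup models (SAP 9.6).** "The different treatment effects across these subgroup variables will be further explored using the alternating logistic regression model detailed in Section 9.3.2", so they do allow for clustering.
- **Planned clustering (SAP 2.4).** It "was given as ICC = 0.54 for simulated arms where 70% or 30% of the worms are without" Wolbachia. For the combination arm, "Minimal clustering (ICC = 0.01) was added to the simulated arm where 90" percent of worms are clear.

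**The concern.** SAP 9.3.2 treats the same worms as correlated for the odds ratios and as independent for the percentages printed beside them. When worms within a subject resemble each other, the pooled percentage varies more than binomial sampling implies, so a plain Wilson interval is too narrow.

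No document makes these intervals a selection rule. They are, however, the only uncertainty the SAP attaches to one arm's or one subgroup's percentage. The odds ratios compare arms with each other. Protocol 2.4.1 also sets the Part 1 target by comparison with doxycycline studies (at least 90% depletion), and Protocol 3.3 selects regimens partly on historical doxycycline data. Both involve reading an arm on its own. An interval that is too narrow makes that reading look firmer than it is, most of all in small district subgroups where two or three subjects can supply all the worms.

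**Working it through.** **Inputs**
- Worms per subject (Protocol 10.3.1, SAP 2.4): 1 to 10 with probabilities 0.20, 0.16, 0.16, 0.16, 0.08, 0.08, 0.08, 0.03, 0.03, 0.02.
- ICC 0.54 at 70% and at 30%, and 0.01 at 90% (same sections).
- 25 evaluable subjects per arm for the combination rule and 17 for proof of concept.
- Assumed, to show a range: ICC 0.10 and 0.30, and any ICC above 0.01 at 90%.

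**Reproducing the plan's power.** Simulation with these inputs and a clustered analysis equivalent in its mean model to alternating logistic regression gives 89.2% with 17 per arm at 70% against 30% (stated 88%). It gives 82.2% with 25 per arm at 90% against 70% with a common association parameter (stated 81%). The inputs are therefore read as the plan intends.

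**Design effect**
- Mean worms per subject: E[m] = 3.79. Also E[m²] = 19.99, so E[m²]/E[m] = 19.99 / 3.79 = 5.27.
- Design effect = 1 + (5.27 − 1) × ICC.
- ICC 0.54: 1 + 4.27 × 0.54 = 3.31. ICC 0.01: 1.04. ICC 0.30: 2.28. ICC 0.10: 1.43.
- 25 subjects give about 25 × 3.79 = 95 worms. At ICC 0.54 they carry the information of about 95 / 3.31 = 29 independent worms.

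**Coverage of the plain interval.** The closed form is 2Φ(1.96 / √design effect) − 1. At ICC 0.54, 1.96 / √3.31 = 1.08, which gives 71.9%. Simulation used beta-binomial worms and 40,000 arms of 25 subjects:

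| ICC | Closed form | 70% clear | 30% clear | 90% clear |
|---|---|---|---|---|
| 0.01 | 94.5% | 94.6% | 94.6% | 94.6% (plan) |
| 0.10 | 89.9% | 89.9% | 90.1% | 90.6% |
| 0.30 | 80.6% | 80.5% | 80.3% | 81.8% |
| 0.54 | 71.9% | 72.0% (plan) | 71.6% (plan) | 72.4% |

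At the plan's values the result does not depend on arm size or on the form of clustering. With 17, 25 or 30 subjects and three different clustering models, coverage is 71.5–72.2% at 70% or 30% and 94.6–94.9% at 90% with ICC 0.01.

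**Subgroups in SAP 9.6**
- The chance that 1, 2, 3, 4 or 5 subjects supply at least 10 worms is 2%, 28%, 65%, 89% and 98%. The threshold therefore admits cells with very few subjects.
- Spread evenly over seven districts (an assumption), an arm has 25 / 7 = 3.6 subjects per district, or 3.6 × 3.79 ≈ 13.5 worms.
- With 3 subjects and at least 10 worms at 70%, plain Wilson covers 65% at ICC 0.54, 78% at 0.30 and 89% at 0.10. At 90% and ICC 0.01 it covers 95%.

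**The case against.** The strongest reply is that these intervals decide nothing. SAP 9.3.2 presents them as an addition, SAP Table 1 makes the odds ratio the summary of both primary estimands, and Protocol 10.9 bases regimen selection on all the data. That is correct, and it limits the weight of the point. It does not make the intervals right.

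Second, the doxycycline target matters most for an arm near 90%, where the plan's ICC of 0.01 makes plain Wilson adequate, and away from 90% the reading rarely changes. At 30%, plain and adjusted intervals both exclude 90% in essentially every simulated arm. At 70% and ICC 0.54, the plain interval excludes 90% in 96% of arms and the adjusted one in 85%, a change in roughly one arm in nine. This is a fair measure of the practical effect on the plan's own scenarios. Between those scenarios the effect is larger: at an assumed 80% and ICC 0.30, exclusion falls from 72% to 51%. The 0.01 is also a planning assumption, and coverage at 90% drops to 82% if the ICC there is 0.30.

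Third, 0.54 is a planning value and not an estimate. That stands, which is why a range is shown. On which arms are exposed, Protocol 10.3.1 ties the 70% and 30% scenarios to Arms A, B and E, while SAP 2.4 applies the 70% scenario to any of Arms A to D. Naming only A, B and E is therefore the cautious reading.

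Fourth, for ITT the SAP analyses 30 imputed datasets, and a cluster-adjusted interval needs a rule for combining them. That is so, but the SAP gives no such rule for the plain Wilson interval either.

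**Conclusion.** The concern holds. On the plan's own worm counts and ICC, the printed 95% intervals for arms at 70% or 30% would miss the true percentage about 28% of the time instead of 5%. At 90% they are sound if the ICC really is 0.01, and too narrow if it is materially higher. In subgroups of three subjects, coverage at 70% and ICC 0.54 is about 65%.

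The size of the error rests on the planned ICC of 0.54; at an assumed 0.10, coverage is 90%. The district example also assumes an even spread, because the documents give no district counts. The defect is confined to descriptive output: the primary odds ratios, their intervals and p-values, and the subgroup and interaction models are unaffected. It should be fixed before the analysis, but it does not threaten the primary test.

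**What to change.** In SAP 9.3.2 (PP and, through 9.3.3, ITT) and 9.6, replace the plain Wilson interval by Wilson on the effective sample size:

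- Effective N = worms / [1 + (Σm²/Σm − 1) × ICC], where m is the number of worms per subject.
- ICC: the ANOVA estimate in that arm, set to 0 if negative. If an arm is at 0% or 100%, use the ICC pooled over the five arms.
- Quantile: t with (subjects in the arm − 1) degrees of freedom in place of z, stated in advance.
- In 9.6, use the arm-level ICC and the same t. Show an interval only if at least 5 subjects contribute worms, in place of the 10-worm rule.
- For ITT, state how the percentage and its interval are combined over the 30 imputed datasets.
- Label the percentages as worm-level and the intervals as adjusted for clustering by subject.

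With 25 subjects this covers 95.0–96.8% at 70% or 30% over ICC 0.01 to 0.54. At 90% it covers 96.7% at ICC 0.01 and 93.0% at an assumed 0.54, so coverage stays slightly low in that last case. With 17 subjects coverage lies in the same overall range, 93–97%. In subgroups of 5 to 12 subjects it is 95–97%. The 5-subject threshold is a judgement and does not come from the documents.

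Per-arm intervals from the fitted alternating logistic regression are a reasonable alternative. That model weights subjects differently, so its estimate need not equal the pooled percentage printed beside it.

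The cost is SAP wording and a few lines of code, with no extra subjects and no change to the primary test or the subgroup models. Mean width rises from 0.18 to 0.32 at 70% with ICC 0.54, and from 0.12 to 0.14 at 90% with ICC 0.01. Fewer subgroup cells will carry an interval.
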